## 3.0 PATIENT SELECTION

### 3.1 Inclusion Criteria

1. At least 18 years of age.
2. Diagnosis of histologically confirmed GBM (WHO grade IV). Subjects with an original histologic diagnosis of low grade glioma or anaplastic glioma (WHO grade II or III) are eligible if a subsequent histological diagnosis of GBM is made.
3. The subject must have completed RT with concurrent TMZ at least 3 months prior to the planned start of treatment on this study UNLESS there is pathological verification of recurrent GBM and at least 4 weeks have elapsed since the end of RT with concurrent TMZ.
4. Experienced first unequivocal progression of GBM by magnetic resonance imaging (MRI) [as assessed via Radiologic Assessment in Neuro-Oncology (RANO) criteria] within 3 months from the last dose of TMZ.
5. Recent resection of recurrent or progressive tumor will be allowed as long as at least 2 weeks have elapsed from the date of surgery and the subject has recovered from the effects of surgery. Evaluable or measurable disease following resection of recurrent tumor is mandated for eligibility into the study.
6. Karnofsky performance status (KPS) of at least 70% (see Appendix A).
7. Willing to remain abstinent from consuming alcohol while on DSF.
8. Recovered from the toxic effects of prior therapy to < grade 2 toxicity per NCI CTCAE version 4 prior to study registration (except lymphopenia). The minimum duration required between prior therapy and initiation of study drug treatment is as follows:
  - a. 12 weeks from completion of radiation therapy UNLESS there is histological confirmation of tumor recurrence in which case at least 4 weeks from completion of RT will suffice

- b. 4 weeks from prior cytotoxic therapy
  - c. 4 weeks from prior experimental drug
  - d. 6 weeks from nitrosoureas
  - e. 3 weeks from procarbazine
  - f. 1 week for non-cytotoxic agents, such as interferon, tamoxifen, and cis-retinoic acid
9. Meets the following laboratory criteria:
- a. Absolute neutrophil count  $\geq$  1,000/mcL
  - b. Platelets  $\geq$  75,000/mcL
  - c. Hemoglobin  $>$  10.0 g/dL (transfusion and/or ESA allowed)
  - d. Total bilirubin and alkaline phosphatase  $\leq$  2x institutional upper limit of normal (ULN)
  - e. Aspartate aminotransferase (AST) and alanine aminotransferase (ALT)  $<$  3 x ULN
  - f. Blood urea nitrogen (BUN) and creatinine  $<$  1.5 x ULN
10. Able to take oral medication.

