### 4.1 Pretreatment Evaluation

Prior to enrollment, patient must have a complete history, physical examination including neurological exam, evaluation of performance status using the KPS, assessment of corticosteroid usage (mg per day), baseline laboratory studies (CBC, BMP, and LFTs), and brain MRI. A baseline MRI scan must be performed within 21 days prior to registration. Women of childbearing potential must have a negative pregnancy test within 14 days of initiation of treatment.

**Commented [SM2]:** Is this really necessary? It may mandate additional costly MRI's.

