### **5.0 RESPONSE ASSESSMENT**

For the purposes of this study, patients should be evaluated for response every 8 weeks

Response and progression will be evaluated in this study using the updated RANO response assessment criteria for high-grade gliomas (Wen, et al. 2010).

Criteria for Determining First Progression Depending on Time from Initial Chemoradiotherapy

First Progression	Definition
Progressive disease < 12 weeks after completion of chemoradiotherapy	Progression can only be defined using diagnostic imaging if there is new enhancement outside of the radiation field (beyond the high-dose region or 80% isodose line) or if there is unequivocal evidence of viable tumor on histopathologic sampling (eg, solid tumor areas [ie, > 70% tumor cell nuclei in areas], high or progressive increase in MIB-1 proliferation index compared with prior biopsy, or evidence for histologic progression or increased anaplasia in tumor). Note: Given the difficulty of differentiating true progression from pseudoprogression, clinical decline alone, in the absence of radiographic or histologic confirmation of progression, will not be sufficient for definition of progressive disease in the first 12 weeks after completion of concurrent chemoradiotherapy.
Progressive disease ≥ 12 weeks after chemoradiotherapy completion	
 
1. New contrast-enhancing lesion outside of radiation field on decreasing, stable, or increasing doses of corticosteroids.
 
2. Increase by ≥ 25% in the sum of the products of perpendicular diameters between the first post-radiotherapy scan, or a subsequent scan with smaller tumor size, and the scan at 12 weeks or later on stable or increasing doses of corticosteroids.
 
3. Clinical deterioration not attributable to concurrent medication or comorbid conditions is sufficient to declare progression on current treatment but not for entry onto a clinical trial for recurrence.
 
4. For patients receiving antiangiogenic therapy, significant increase in T2/FLAIR non-enhancing lesion may also be considered progressive disease. The increased T2/FLAIR must have occurred with the patient on stable or increasing doses of corticosteroids compared with baseline scan or best response after initiation of therapy and not be a result of comorbid events (eg, effects of radiation therapy, demyelination, ischemic injury, infection, seizures, postoperative changes, or other treatment effects).
 

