Criteria for Response Assessment Incorporating MRI and Clinical Factors (Adapted from (Wen, et al. 2010).

Response	Criteria
Complete response	
 
• Requires all of the following: complete disappearance of all enhancing measurable and non-measurable disease sustained for at least 4 weeks.
 
• No new lesions; stable or improved non-enhancing (T2/FLAIR) lesions.
 
• Patients must be off corticosteroids (or on physiologic replacement doses only) and stable or improved clinically. Note: Patients with non-measurable disease only cannot have a complete response; the best response possible is stable disease.
 

Partial response	
Requires all of the following:
 
 
• ≥ 50% decrease compared with baseline in the sum of products of perpendicular diameters of all measurable enhancing lesions sustained for at least 4 weeks.
 
• No progression of non-measurable disease.
 

Response	Criteria
	
 
Stable or improved non-enhancing (T2/FLAIR) lesions on same or lower dose of corticosteroids compared with baseline scan; the corticosteroid dose at the time of the scan evaluation should be no greater than the dose at time of baseline scan.
 
Stable or improved clinically. Note: Patients with non-measurable disease only cannot have a partial response; the best response possible is stable disease.
 

Stable disease	Requires all of the following: 
 
Does not qualify for complete response, partial response, or progression.
 
Stable non-enhancing (T2/FLAIR) lesions on same or lower dose of corticosteroids compared with baseline scan. In the event that the corticosteroid dose was increased for new symptoms and signs without confirmation of disease progression on neuroimaging, and subsequent follow-up imaging shows that this increase in corticosteroids was required because of disease progression, the last scan considered to show stable disease will be the scan obtained when the corticosteroid dose was equivalent to the baseline dose.
 

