Progression	Defined by any of the following: 
 
<math>\geq 25\%</math> increase in sum of the products of perpendicular diameters of enhancing lesions compared with the smallest tumor measurement obtained either at baseline (if no decrease) or best response, on stable or increasing doses of corticosteroids*. The absolute increase in any dimension must be at least 5mm when calculating the products.
 
Significant increase in T2/FLAIR non-enhancing lesion on stable or increasing doses of corticosteroids compared with baseline scan or best response after initiation of therapy* not caused by comorbid events (e.g. radiation therapy, demyelination, ischemic injury, infection, seizures, postoperative changes, or other treatment effects).
 
Any new measurable lesion.
 
Clear clinical deterioration not attributable to other causes apart from the tumor (e.g. seizures, medication adverse effects, complications of therapy, cerebrovascular events, infection, and so on) or changes in corticosteroid dose.
 
Failure to return for evaluation as a result of death or deteriorating condition; or clear progression of non-measurable disease.
 

- NOTE. All measurable and non-measurable lesions must be assessed using the same techniques as at baseline.
- Abbreviations: MRI, magnetic resonance imaging; FLAIR, fluid-attenuated inversion recovery.
- Stable doses of corticosteroids include patients not on corticosteroids.

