## 10.0 STUDY CALENDAR

Screening/baseline evaluations are to be conducted within 2 weeks prior to start of protocol therapy. Scans and x-rays must be done no more than 4 weeks prior to the start of the protocol therapy. Each treatment cycle is 28 days.

	Screening / Baseline	Within 10 Days Before Each Cycle	End of Every Even-Numbered Cycle	End of Treatment	Follow-Up 
Informed consent	X				
H&P incl. neurologic exam, KPS	X	X		X	
Evaluation of corticosteroid usage	X	X			
CBC	X				
LFTs	X				
Brain MRI	X		X 	X	
Temozolomide		Days 1-5 of each cycle 			
Disulfiram		Days 1-28 of each cycle 			
Copper gluconate		Days 1-28 of each cycle 			
AE assessment	X ----- X 				

1. Follow-up will be as clinically indicated. A chart review will be done at 2 years after the last dose of DSF to look for progression and survival.
2. Women of childbearing potential only.
3. A confirmatory MRI should be considered in 4-8 weeks after documentation of complete response (CR) or partial response (PR) if consistent with the institutional standard of care
4. To be taken at bedtime on an empty stomach. Must not be taken within an hour of DSF.
5. To be taken three times a day with meals.
6. AEs will be tracked for 30 days after the last dose of DSF.

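### No settled corticosteroid dose is required before the baseline MRI, so a partial response that follows a dose rise just before baseline is not screened out of the uncontrolled ORR

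*Combined protocol and SAP*

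**What the plan says.** Section 3.1, item 4, admits patients who have "Experienced first unequivocal progression of GBM by magnetic resonance imaging (MRI") by RANO criteria within 3 months of the last temozolomide dose. The first-progression table in section 5.0 accepts growth seen on "the scan at 12 weeks or later on stable or increasing doses of corticosteroids", so a dose rise at progression does not bar entry. Neither 3.1 nor 3.2 has a corticosteroid criterion.

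Section 4.1 asks for "assessment of corticosteroid usage (mg per day") before enrollment, without a stability period. It times the scan to registration: "A baseline MRI scan must be performed within 21 days prior to registration". The Study Calendar (10.0) times it to treatment: "Scans and x-rays must be done no more than 4 weeks prior to the start of the protocol therapy". Neither window is tied to a settled dose.

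For PR, section 5.0 requires at least a 50% "decrease compared with baseline in the sum of products of perpendicular diameters of all measurable enhancing lesions sustained for at least 4 weeks". It also requires no progression of non-measurable disease, stable or improved T2/FLAIR, and stable or improved clinical status. Its dose condition is that "the corticosteroid dose at the time of the scan evaluation should be no greater than the dose at time of baseline scan". Complete response (CR) is stricter: the patient must be off corticosteroids or on physiologic replacement only. Section 12.1 makes ORR (CR or PR) co-primary with PFS6.

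**The concern.** The response criteria themselves treat corticosteroid dose as something that can change the scan, which is why the CR, PR, stable disease and progression rows all mention it. The PR safeguard works in one direction in time. It blocks a response when the dose rises after baseline and is still higher at the evaluation scan. It cannot detect a rise just before baseline, because the two doses it compares are then equal.

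For example, the dose is raised two days before the baseline MRI and held, and at week 8 the enhancing area has halved. The dose condition is met even though the corticosteroid may explain some or all of the change. Recording the dose at each visit (section 4.4) does not help, because no rule uses the dose history before baseline.

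The trial has one arm and 20 patients, and its hypothesis is framed as an improvement in ORR or in PFS6. A small number of misattributed responses could therefore decide the ORR result.

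**Working it through.** **1. Which PR conditions could catch the case.** The case is a dose raised just before baseline and then held.
- Dose condition: met, since the doses at the two scans agree.
- Decrease of at least 50%, sustained at least 4 weeks: this removes small or brief shrinkage, but not an effect that lasts while the dose is held. The Study Calendar asks only that a confirmatory MRI be considered, where that is local standard of care.
- T2/FLAIR and clinical status: both need only be stable or improved. The cause of improvement is not examined.
- Recorded dose: the calendar places screening evaluations within 2 weeks of starting therapy but allows scans up to 4 weeks before. The screening dose need not be the dose on the scan date.

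No condition removes the case by design.

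**2. The plan's own design.** Section 12.1 gives n = 20, a one-sided exact test, alpha about 0.10, power 80%, and ORR 5% against 20%. It states no cutoff. With X ~ Binomial(20, p):

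| Success if X is at least | alpha (p = 0.05) | power (p = 0.20) |
|---|---|---|
| 2 | 0.264 | 0.931 |
| 3 | 0.0755 | 0.794 |
| 4 | 0.016 | 0.589 |

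A cutoff of 3 comes closest to the stated error rates, so I assume it. At p = 0.05, 1 − (0.35849 + 0.37735 + 0.18868) = 0.0755.

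**3. Effect of steroid-only PRs.** Suppose k patients had a rise just before baseline, and each would otherwise be a non-responder with chance q of a steroid-only PR. Their response probability is 0.05 + 0.95q, and the other 20 − k respond at 0.05. Both k and q are assumptions; the documents give neither.

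- k = 1, q = 0.10: response probability 0.05 + 0.95 × 0.10 = 0.145. With Y ~ Binomial(19, 0.05), P = P(Y ≥ 3) + 0.145 × P(Y = 2) = 0.06655 + 0.145 × 0.17875 = 0.0925.
- k = 3, q = 0.10: the three patients give 0, 1 or 2 responses with probability 0.62503, 0.31800 and 0.05393. The other 17 give at most 2, at most 1 or exactly 0 with probability 0.94975, 0.79223 and 0.41812. P = 1 − (0.62503 × 0.94975 + 0.31800 × 0.79223 + 0.05393 × 0.41812) = 1 − 0.8681 = 0.132.
- k = 3, q = 0.20 and 0.30 (response probability 0.24 and 0.335), same formula: 0.199 and 0.275.
- One certain false PR: at least 2 of the other 19 must respond, so P = 1 − 0.37735 − 0.37735 = 0.245.

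| Scenario (true ORR 5%, cutoff 3 of 20) | Chance of a false-positive ORR |
|---|---|
| No steroid-only PR possible | 0.0755 |
| 1 patient, 10% | 0.0925 |
| 3 patients, 10% / 20% / 30% | 0.132 / 0.199 / 0.275 |
| 1 certain false PR | 0.245 |

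**4. PFS6.** The size criterion for progression is at least 25% growth from the smallest measurement, at baseline if there has been no decrease and otherwise at best response, "on stable or increasing doses of corticosteroids". If steroids shrink the lesion by the first scan, that smaller size becomes the reference and the baseline drops out.

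**The case against.** The PR row is an adopted RANO rule and is demanding: a halving of area held for 4 weeks, without worsening on T2/FLAIR or clinically. Nothing in the documents shows how often corticosteroids alone achieve that. The false-positive figures rest on assumed inputs, and milder ones stay inside the design's alpha of about 0.10: one patient at 10% gives about 0.09. The figure of 0.245 would follow from any single misclassified response, whatever its cause. The 5% null comes from a historical study whose steroid rules are not visible here and may already include such cases. All of this stands. It limits the size of the problem but does not close the gap.

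A reader might also draw stronger conclusions, which the documents do not support:
- *All steroid-related shrinkage counts as response.* Only shrinkage meeting every PR condition does, and CR is protected by its own steroid rule.
- *Patients enter just after progression, with doses on the move.* Item 4 ties progression to the last temozolomide dose, not to enrollment. For re-resected patients, item 5 requires at least 2 weeks and recovery from surgery. Nothing shows that doses would be rising.
- *Every steroid rule compares only two scan-day doses.* That describes the PR row. The stable disease row looks back at increases between scans.
- *An inflated baseline raises PFS6 throughout.* The smallest-measurement reference confines this mainly to the first scan, where growth and steroid shrinkage could offset each other. New lesions, T2/FLAIR increase and clinical deterioration still count as progression on their own.

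**Conclusion.** The gap is real and concerns PR, and through it the co-primary ORR. No section requires a settled dose before the baseline MRI, and the PR rule cannot see a rise that precedes it. CR is not affected, and any effect on PFS6 is mainly limited to the first scan.

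The size is unknown. With a derived cutoff of 3 of 20, a true ORR of 5% and independent patients, the false-positive chance moves from 0.0755 to between about 0.09 and 0.275 over the scenarios shown. The low end is within the planned alpha and the upper part well above it. This is a reason for an inexpensive tightening before enrollment. It is not evidence that the ORR result will be wrong.

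**What to change.** 1. In section 4.1, accept as the RANO baseline an MRI done after the corticosteroid dose has been unchanged or falling for a number of days that the sponsor fixes in advance. This governs which scan counts as baseline; steroid dosing stays with the treating physician.
2. Add a baseline field for the dose on the scan date and any dose change in the defined period before it.
3. In section 12.1, pre-specify an ORR sensitivity analysis that counts as non-responders any patients whose dose rose in that period, for example where a repeat scan was not feasible. No matching PFS6 analysis is proposed, since non-responder has no defined meaning for that endpoint.
4. Reconcile the window of 21 days before registration (4.1) with that of 4 weeks before therapy (10.0), so that it is clear which scans can serve as baseline.

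The cost is one sentence, one field and one analysis; the sample-size inputs do not change. Some patients would wait some days, and a patient whose progression scan followed a recent rise may need a repeat MRI. A margin comment in section 4.1 already questions the expense of extra scans. If that burden is not acceptable, items 2 and 3 alone still address the bias, by showing whether the ORR conclusion depends on such patients.

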### 3.2 Exclusion Criteria

1. Radiographic evidence of leptomeningeal dissemination, gliomatosis cerebri, infratentorial tumor, or metastatic disease to sites remote from the supratentorial brain.
2. Enrolled in another clinical trial testing a novel therapy or drug.
3. Received more than one course of radiation therapy or more than a total dose of 75 Gy. Subjects may have received radiosurgery as part of the initial therapy (i.e., in addition to one course of radiation therapy); however, the dose used for the radiosurgery counts against the total dose limit listed above.
4. History of allergic reaction to DSF or Cu.
5. Treatment with the following medications that may interfere with metabolism of DSF: warfarin, theophylline, amitriptyline, isoniazid, metronidazole, phenytoin, Phenobarbital, chlorzoxazone, halothane, imipramine, chlordiazepoxide, diazepam. (Note: lorazepam and oxazepam are not affected by the P450 system and are not contraindicated with DSF).
6. Active infection including known Acquired Immunodeficiency Syndrome (AIDS) or Hepatitis C or with a fever  $\geq$  38.5°C within 3 days prior to the study enrollment.
7. Active or severe hepatic disease.
8. Grade 2 or higher peripheral neuropathy or ataxia per NCI CTCAE version 4.
9. History of idiopathic seizure disorder schizophrenia, or psychosis unrelated to glioblastoma, corticosteroid, or anti-epileptic medications.
10. History of Wilson's disease.
11. History of hemochromatosis.

Commented [SM1]: Why?

12. Pregnant and breastfeeding women will be excluded because of the unknown effect of DSF on fetal development (and because of use of temozolomide).

### 3.3 Inclusion of Women and Minorities

Both men and women and members of all races and ethnic groups are eligible for this trial.

## 4.0 TREATMENT PLAN

This multi-center study is a single arm, open-label, phase II study of DSF-Cu in combination with TMZ for recurrent TMZ-resistant GBM patients after their first relapse from TMZ.

### 4.1 Pretreatment Evaluation

Prior to enrollment, patient must have a complete history, physical examination including neurological exam, evaluation of performance status using the KPS, assessment of corticosteroid usage (mg per day), baseline laboratory studies (CBC, BMP, and LFTs), and brain MRI. A baseline MRI scan must be performed within 21 days prior to registration. Women of childbearing potential must have a negative pregnancy test within 14 days of initiation of treatment.

**Commented [SM2]:** Is this really necessary? It may mandate additional costly MRI's.

### 4.2 Disulfiram and Copper Dosing

Two study drugs will be provided: disulfiram in 40 mg capsules and copper gluconate in 1.5 mg capsules. DSF will be given at 80 mg (two capsules) three times daily with meals. Copper gluconate will be taken with each dose of DSF at a dose of 1.5 mg (one capsule) to improve the potential effect of DSF on GBM tumors. Although Washington University's previous phase 1 study has demonstrated MTD of DSF to be 500 mg per day in combination with TMZ, the current protocol uses a TID administration with concurrent Cu, which may improve absorption and bioavailability. Thus, the DSF dose will be a total of 240 mg per day. If administration of DSF and Cu together causes gastrointestinal discomfort, then Cu will be administered 30 minutes before the DSF dose. If a patient misses a dose, s/he should be instructed not to make up that dose but should instead resume dosing with the next scheduled dose. Patients will be instructed to bring all unused drug and the completed medication diary (Appendix B) to each study visit for assessment of compliance.

### 4.3 Temozolomide Dosing

TMZ should be continued according to the standard adjuvant dose that the patient has been receiving. TMZ will not be provided by the study sponsor. Dosage is typically 150-200 mg/m^2 PO per day on Days 1-5 of every 28-day cycle. If the patient was receiving adjuvant TMZ with an experimental agent, only TMZ should be continued. TMZ should be taken at bedtime on an empty stomach and should not be taken within one hour of DSF

administration. Patients will be instructed to bring their completed medication diary (Appendix C) to the study visit for assessment of compliance.

#### 4.4 Study Evaluations

Consistent with institutional standard of care, patients will be seen approximately every 4 weeks and typically within 10 days before the start of the next cycle. At each visit, a KPS evaluation and corticosteroid usage (mg per day) will be recorded. Brain MRI will be obtained every 8 weeks to assess for radiological response.

Patients are evaluated for adverse events for 30 days from the last treatment of DSF-Cu, or until death, whichever occurs first. Patients removed from study for unacceptable adverse events will be followed until resolution or stabilization of the adverse event.

